13.4 Vital Signs and Weight

The PCS criteria used for vital signs and weight are the Lundbeck standard PCS criteria shown in [Table 3](#).

13.5 ECGs

The PCS criteria used for the ECG parameters are the Lundbeck standard PCS criteria described in [Table 4](#).

In addition to the tables and listings specified in section [13.2](#), the absolute values and changes from Baseline in QTcF will also be summarized categorically by visit and treatment. The categories that will be used are as follows for the absolute QTcF values:

- QTcF interval < 450 msec
- QTcF interval 450 - 480 msec
- QTcF interval > 480 - 500 msec
- QTcF interval > 500 msec

The categories that will be used for the change from baseline QTcF values are:

- QTcF interval increase from baseline > 30 msec
- QTcF interval increase from baseline > 60 msec

Furthermore, the number and percentage of participants being classified as having either a *normal*, *abnormal but not clinically significant*, or *abnormal and clinically significant* ECG result based on the overall interpretation of the ECG from the investigator will be summarized by visit and treatment group.

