13.2 General Methodology for Other Safety Data

Unless otherwise specified, tables, graphs, and listings will be based on the APTS.

All the tables will be presented by treatment group.

The denominators for the summaries of a given variable will be based on the number of participants with non-missing values at a given visit or during the assessment period.

Descriptive statistics for the safety variables, both absolute values and changes from baseline, will be presented by visit.

The number and percentage of participants with at least one PCS value at any post-baseline assessment time point will be summarized by variable. All available assessments will be included in the evaluation of PCS values.

The number and percentage of participants with values out-of-reference range and/or PCS range will be summarized by variable, visit, and last post-baseline assessment.

For participants with post-baseline PCS values, listings will be provided including all the values for those participants for the variable, with flagging of PCS values and out-of-reference-range values.

All the adverse events occurring in participants with post-baseline PCS values will be listed by treatment group and participant screening number; the listing will include the PCS value, the assessment date, the change from baseline in PCS value, the preferred term for the adverse event, and the start date and stop date of the adverse event. The PCS values and adverse events will be listed in chronological order according to assessment date and the start date of the adverse event.

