22.2.1 Safety Variables

Laboratory Tests, Vital Signs, Body Weight, ECG and C-SSRS

Assessments at unscheduled visits and withdrawal visits will be assigned to a nominal visit, according to the visit windowing specified in Panel 6. Assessments for participants not receiving an infusion of IMP will be assigned to Visit 2 (Baseline).

Panel 6 Visit Windows - Laboratory Tests, Vital Signs, Body Weight, ECG and C-SSRS

Nominal Visit Number	Nominal Visit Week	Nominal Visit Day	Time Window
V1 (Screening Visit)	-4	-28	Day -28 and before IMP infusion
V2 (Baseline Visit)	0	0	Same day as IMP infusion (Day 0) and prior to IMP infusion on that date
V3	2	14	After start of IMP infusion to Day 21
V4	4	28	Day 22 to Day 41 after start of IMP infusion

Nominal Visit Number	Nominal Visit Week	Nominal Visit Day	Time Window
V5	8	56	Day 42 to Day 69 after start of IMP infusion
V6	12	84	Day 70 to Day 98 after start of IMP infusion

If there is more than one assessment at a visit (either due to multiple assessments or because an unscheduled or withdrawal visit assessment is mapped to a nominal visit with an already existing value) the value that will be used in summary tables by visit will be the one closest to the nominal day for the visit but prioritizing values from scheduled visits above values from withdrawal or unscheduled visits. In the ordering of multiple values, assessments without recorded time will come after assessments with recorded time and the first in the ordering will be selected.

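### QTcF categories are tabulated only by visit with scheduled ECGs taking precedence, so an unscheduled or withdrawal QTcF of 450-500 ms, or a rise of 31-60 ms, can be missing from them, and no table counts participants who ever reached a category

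*SAP*

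**What the plan says.** SAP 13.5 defines four absolute QTcF categories, the third being "QTcF interval > 480 - 500 msec", and two change categories, the first being "QTcF interval increase from baseline > 30 msec". Both sets are reported "in QTcF will also be summarized categorically by visit and treatment". The section has no row for the worst or any post-baseline value. The investigator's overall ECG interpretation is also summarized by visit.

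SAP 22.2.1 determines which ECG enters a by-visit table. "Assessments at unscheduled visits and withdrawal visits will be assigned to a nominal visit", using the windows in its visit-window panel: start of infusion to Day 21 for Visit 3, Days 22-41 for Visit 4, Days 42-69 for Visit 5 and Days 70-98 for Visit 6. If a window holds more than one assessment, only one enters the by-visit tables. Nearness to the nominal day decides, but subordinate to a second criterion: "prioritizing values from scheduled visits above values from withdrawal or unscheduled visits".

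SAP 13.2 does plan an any-time count, for PCS values only: "participants with at least one PCS value at any post-baseline assessment time point will be summarized by variable". The same section settles which ECGs feed that count: "All available assessments will be included in the evaluation of PCS values". Listings of values are limited to participants with a post-baseline PCS value. Out-of-range values are tabulated by visit and at the last post-baseline assessment. SAP Appendix V, Table 4 gives the high PCS limits: above 500 ms or an increase above 60 ms for both QTcF and QTcB, and 500 ms or more for QT.

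**The concern.** Category tables for QTcF exist to show how many participants had a prolonged interval or a notable rise. Here the selection rule does not look at the size of the reading: a higher unscheduled or withdrawal value gives way to a lower scheduled one in the same window. The any-time PCS table would recover it only above limits that sit beyond the middle categories of SAP 13.5.

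A second gap needs no unscheduled ECG. By-visit counts cannot be added across visits. One participant at 485 ms on three visits gives the same counts as three participants at 485 ms on one visit each, if those visits are the same three. The number who ever exceeded 480 ms, or ever rose by more than 30 ms, cannot be read from any planned table.

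What is at stake is the completeness of a descriptive safety display. No efficacy result and no test depends on it.

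**Working it through.** The plan gives no figure to reproduce. The check applies its rules to example ECG series.

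**Rules used**
1. Windows and selection from SAP 22.2.1: a scheduled value first, then the value nearest the nominal day.
2. Categories from SAP 13.5.
3. PCS limits from SAP Appendix V, Table 4, applied to every assessment (SAP 13.2).
4. Entry limit: Protocol 5.3, exclusion criterion 29, excludes QTc above 450 ms at screening, so the baselines below are possible.
5. Protocol 8.8 allows ECGs at unscheduled visits.

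**Example series** (all values in ms)

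| Case | Baseline | Extra ECG | Scheduled ECGs | Category tables | QTcF PCS |
|---|---|---|---|---|---|
| A | 440 | 490, Day 10 (rise 50) | 434-436 | below 450, no rise above 30, at every visit | no |
| B | 400 | 445, Day 33 (rise 45) | 402-405 | below 450, no rise above 30, at every visit | no |
| C | 415 | 490, Day 10 (rise 75) | 420 | extra ECG not shown | yes |
| D | 440 | 490, Day 33, no scheduled ECG in the Visit 4 window | 434-436 at the other visits | shown at Visit 4 as above 480 to 500 | no |
| E | 440 | 490, Day 88, the last ECG | 434-436 | extra ECG not shown | no |
| F | 450 | 505, Day 10 (rise 55) | 434-436 | extra ECG not shown | yes |

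A and B are the gap. C and F are recovered by the PCS table. D shows that the gap requires a scheduled ECG in the same window. E may appear in the last-assessment out-of-range table, if the last assessment can be an unscheduled one and 490 ms is above the reference range; the documents state neither.

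**Baselines at which 481-500 ms escapes the QTcF limits.** The rise must be at most 60, so baseline must be at least the value minus 60: 481 - 60 = 421, 490 - 60 = 430, 500 - 60 = 440. All lie within the 450 ms entry limit. Any rise of 31-60 with QTcF at or below 500 escapes the QTcF limits.

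**The other two ECG limits.** Assuming the standard formulas, with HR the heart rate in beats/min, QTcB = QTcF x (HR/60)^(1/6) and QT = QTcF x (60/HR)^(1/3). So QTcB exceeds 500 when HR > 60 x (500/QTcF)^6, and QT reaches 500 when HR <= 60 / (500/QTcF)^3.

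| QTcF | QTcB above 500 if HR above | QT at least 500 if HR at most | Escapes both at HR |
|---|---|---|---|
| 450 | 112.9 | 43.7 | 44-112 |
| 481 | 75.7 | 53.4 | 54-75 |
| 490 | 67.7 | 56.5 | 57-67 |
| 495 | 63.7 | 58.2 | 59-63 |
| 500 | 60.0 | 60.0 | none |

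The QTcB rise limit can catch more, depending on heart rate at both ECGs. In case B, with HR 60 at baseline (QTcB 400) and HR 80 at the extra ECG, QTcB is 445 x (80/60)^(1/6) = 466.9, a rise of 66.9, which is PCS. With HR 60 at both ECGs, QT, QTcB and QTcF coincide, and neither A (490, rise 50) nor B (445, rise 45) meets any of the three limits.

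**Withdrawal ECGs.** Protocol 8.9 applies the Withdrawal Visit only before Week 4, and moves it to Week 4 for withdrawals between Weeks 3 and 4. The overlap therefore arises mainly when someone withdraws after Visit 3 but by Day 21. For example, a scheduled ECG on Day 14 displaces a withdrawal ECG on Day 18. If the participant then attends the Week 12 safety visit, which includes an ECG, the last-assessment table does not recover the Day 18 value.

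**The case against.** The strongest reply is that the SAP already has an any-time safety net. The QTcF categories are stated to be additional to the SAP 13.2 outputs, and the PCS table uses every assessment and applies QTcB and QT limits as well as QTcF. That net is wider than the QTcF limits alone suggest: near 500 ms few heart rates escape it, and at exactly 500 ms none does. An ECG judged abnormal and clinically significant must also be recorded as an adverse event (Protocol 9.5.5), and a data monitoring committee reviews safety data during the trial. One value per participant per visit is a normal requirement for a by-visit table, the ECG summaries are descriptive, and nothing in the SAP is contradictory.

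Most of this stands, and it rules out stronger readings:
- A reader might infer that such a value is absent from every table. The documents do not support that: adverse event tables, the PCS tables for QTcB or QT, and the last-assessment table are all possible routes.
- A reader might infer that the counts are understated. That is not shown, because the number of unscheduled ECGs is not given.
- A reader might infer that unscheduled ECGs are the worrying ones. Protocol 8.8 says only that such visits occur if needed and may include an ECG.

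The reply does not close the gap. A value caught through QTcB or QT is counted under that variable, not in the QTcF categories. Values around 450-481 ms and rises of 31-60 ms escape over a wide range of heart rates. The inability to count participants who ever reached a category is untouched.

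**Conclusion.** The point holds as a minor one. When a scheduled ECG shares the window, an unscheduled or withdrawal QTcF of 450-500 ms or a rise of 31-60 ms can be missing from the QTcF category tables. It is then also missing from the any-time PCS table and listing unless a QTcF, QTcB or QT limit is met. Separately, no planned table gives the number of participants who ever exceeded 480 ms or rose by more than 30 ms, even from scheduled ECGs alone.

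The counts can be understated, by an amount the documents do not allow anyone to estimate. The conclusion rests on the selection rule applying to the SAP 13.5 tables, which follows from their being by visit. The heart-rate ranges rest on the standard Bazett and Fridericia formulas.

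**What to change.** Add to SAP 13.5 a maximum post-baseline row in both QTcF category tables (absolute value and change from baseline), counting each participant once and using all post-baseline ECGs: scheduled, unscheduled and withdrawal. The by-visit rows and the SAP 22.2.1 rule can stay as they are.

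The SAP already works this way elsewhere: SAP 13.3.3 counts each participant once at the maximum liver test value across post-baseline visits, and SAP 13.6.1 reports the most severe C-SSRS item over the whole period. The cost is one sentence in the SAP and one extra row per table, with no new data.

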13.6 Other Safety Endpoints

13.6.1 Columbia-Suicide Severity Rating Scale (C-SSRS) Scores

The C-SSRS was administered:

- for lifetime (using the *Baseline/Screening Version*) – the C-SSRS assessment at screening that collects a lifetime recall
- for the past 12 months at screening (using the *Baseline/Screening Version*) – the C-SSRS assessment at screening that focuses on the last 12 months
- at baseline (using the *Since Last Visit Version*) – the C-SSRS assessment at baseline that collects information since the previous visit

- post-baseline (using the *Since Last Visit Version*) – the C-SSRS assessments after baseline

The numbers and percentages of participants with lifetime, past 12 months, baseline, or post-baseline suicide-related events based on the C-SSRS will be summarized by treatment group. For each summary, the most severe item with an answer “Yes” for each participant according to the ordering given in [Panel 6](#) is displayed. For the post-baseline assessments, the summaries will be by treatment group and period and the most severe item with an answer “Yes” for the whole period for each participant related to suicidal ideation and/or behaviour will be summarized.

The number and percentage of participants with *no suicidal ideation or behaviour* will be included in the summaries.

Panel 6 C-SSRS Scores

C-SSRS Score		Related to:
1	Wish to be dead	Suicidal ideation
2	Non-specific active suicidal thoughts	
3	Active suicidal ideation with any methods (not plan) without intent to act	
4	Active suicidal ideation with some intent to act, without specific plan	
5	Active suicidal ideation with specific plan and intent	
6	Preparatory acts or behaviour	Suicidal behaviour
7	Aborted attempt	
8	Interrupted attempt	
9	Non-fatal suicide attempt	
10	Completed suicide (only applicable for the post-baseline assessments)	

The C-SSRS scores will be summarized by visit based on the APTS for participants with at least one post-baseline C-SSRS assessment, regardless of whether they had a baseline C-SSRS assessment.

Missing C-SSRS scores will not be imputed.

Positive responses to *non-suicidal self-injurious behaviour* will be summarized separately.

For participants with any post-baseline suicidal behaviour (C-SSRS scores of 6 to 10), listings will be provided including all C-SSRS scores for those participants; C-SSRS scores related to suicidal behaviour will be flagged.

14 CCI [Redacted]

CCI [Redacted]

CCI

15 Pharmacokinetic/Pharmacodynamic Analyses

CCI

16 CCI

CCI

17 Blinded Data Reviews

The quality of the trial will be overseen by performing blinded data reviews during the conduct of the trial. The reviews may include, but are not limited to, data quality, protocol adherence, and the appropriateness of design assumptions, including the sample size assumptions.

An independent Safety Data Monitoring Committee (DMC) will regularly monitor the participants' safety data according to the *DMC Charter*. The DMC will have access to unblinded information for the double-blind treatment for each participant. Members of the DMC will not be involved in other trial-related tasks.

18 Interim Analyses

No interim analyses are planned.

19 Sample Size Considerations

Simulations were used to determine a sample size that ensured at least 80% power at a one-sided 5% significance level for detecting an effect of 2.1 on the CCI dose when using an ANCOVA with baseline MMD as a covariate and treatment and population (EM or CM) as fixed factors and allowing for stopping for futility. A population with 30% EM and 70% CM participants was assumed with standard deviations of 3.8 and 6.1, respectively, which resulted in a standard deviation of 5.6 for the full population. The resulting required sample size is 86 participants per arm for the CCI dose and placebo. No formal power calculation was performed for the CCI dose. A sample size of 43 per arm was considered sufficient to evaluate the relevant endpoints for this dose, which results in a randomization ratio of 2:1:2. Adjusting for an expected 5% withdrawal rate, a total sample size of 230 will be required.

The cap of 30% for the EM population results in a similar precision (standard error) for the treatment estimates for the EM and CM populations.

Simulations are based on 10000 runs.

20 Statistical Software

The statistical software used will be SAS®, Version 9.4 or later.

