16.10 Sample Size and Power

Simulations were used to determine a sample size that ensured at least 80% power at a one-sided 5% significance level for detecting an effect of 2.1 on the CCI dose when using an ANCOVA with baseline MMD as a covariate and treatment and population (EM or CM) as fixed factors. A population with 30% EM and 70% CM patients was assumed with standard deviations of 3.8 and 6.1, respectively, which resulted in a standard deviation of 5.6 for the full population. The resulting required sample size is 86 patients per arm for the CCI dose and placebo. No formal power calculation was performed for the CCI dose. A sample size of 43 per arm was considered sufficient to evaluate the relevant endpoints for this dose, which results in a randomization ratio of 2:1:2. Adjusting for an expected 5% dropout rate, a total sample size of 230 will be required.

The cap of 30% for the EM population results in a similar precision (standard error) for the treatment estimates for the EM and CM populations.

Simulations are based on 10000 runs.

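### Does the leftover mention of a futility stop in the SAP's sample size section undermine the stated 80% power?

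*SAP*

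**What the plan says.** SAP Section 19 (Sample Size Considerations) reports simulations that gave "at least 80% power at a one-sided 5% significance level" for "detecting an effect of 2.1 on the CCI dose". The model was an "ANCOVA with baseline MMD as a covariate and treatment and population (EM or CM) as fixed factors", and the sentence closes by adding a futility stop: "as fixed factors and allowing for stopping for futility". The variance input is: "A population with 30% EM and 70% CM participants was assumed with standard deviations of 3.8 and 6.1, respectively". The result is: "The resulting required sample size is 86 participants per arm for the CCI dose and placebo".

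SAP Section 18 (Interim Analyses) consists of one statement: "No interim analyses are planned".

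Protocol Section 16.10 (Sample Size and Power) gives the same effect, SDs, 86 per arm, total of 230 and 10000 runs, without the futility clause. Like the SAP, it says of the two SDs: "which resulted in a standard deviation of 5.6 for the full population". The change summary of protocol Edition 3.0 (Major Changes Since Last Edition) explains the difference. A non-binding futility interim had been planned, it will not be carried out, and all references to it were taken out of the protocol.

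**The concern.** One sample size, with one power claim, is attached to two designs: one with a futility stop (SAP) and one without (protocol). A futility stop costs power. If 86 per arm is just enough without a stop, it might fall short with one, and then one of the two statements could not be the simulated result.

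The quoted full-population SD adds to the doubt. With 5.6 in place of 5.51, 86 per arm falls slightly below 80%.

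Power matters here because this is a proof-of-concept trial with a single type-1-controlled comparison, and a null result would be judged against it. A futility stop mentioned next to a statement that there is no interim could also lead a reader to ask whether an unblinded efficacy look took place.

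**Working it through.** **Inputs.** SAP Section 19 and protocol Section 16.10 give: difference 2.1 MMDs; one-sided 5%; power at least 80%; EM 30% with SD 3.8; CM 70% with SD 6.1; 1:1 for the powered comparison; 5% dropout. Neither document gives a futility rule, its timing, or the correlation between baseline MMDs and the outcome.

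**1. The SD that fits the model.** The model has population (EM or CM) as a factor, so the residual SD is the within-population one:

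sqrt(0.3 × 3.8² + 0.7 × 6.1²) = sqrt(4.332 + 26.047) = sqrt(30.379) = 5.51.

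The quoted 5.6 also contains the difference between the EM and CM means. The implied difference is sqrt((5.6² − 30.379) / (0.3 × 0.7)) = sqrt(0.981 / 0.21) = 2.16 days, which the population factor removes.

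**2. Reproducing 86 per arm, no interim.**

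n = 2 × 30.379 × (1.645 + 0.842)² / 2.1² = 85.2, so 86 per arm.

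Power at 86: 2.1 / (5.51 × sqrt(2/86)) = 2.498, and 2.498 − 1.645 = 0.853, which gives 80.3%. The noncentral t distribution gives 80.1%. A 20,000-run ANCOVA simulation with 86:86:43 patients and a baseline unrelated to outcome gave 79.5%, with a Monte Carlo standard error of sqrt(0.8 × 0.2 / 20000) = 0.3 points.

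**3. Dropout.** 86/0.95 = 90.5 and 43/0.95 = 45.3, which rounds up to 46. At 2:1:2 this makes 92 + 46 + 92 = 230, as stated.

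**4. If SD 5.6 were used.** n = 88 on the normal approximation, with 79.2% power at 86 (78.9% by noncentral t, which needs 89). This SD does not match the stated model, and the gap is about one point.

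**5. Effect of the baseline covariate.** Both documents include baseline MMDs in the power model. With an assumed correlation r, the residual SD is 5.51 × sqrt(1 − r²). Power at 86 with no stop is 81.7% at r = 0.2, 83.5% at r = 0.3 and 86.0% at r = 0.4.

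**6. Effect of a futility stop.** All rules below are assumptions, because none is in the documents. The figures use 86 per arm, SD 5.51, r = 0 and the normal approximation.

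| Assumed rule, at 30% to 60% of the information | Power |
|---|---|
| No stop | 80.3% |
| Conditional power below 10% to 20% under the design effect | 79.9% to 80.3% |
| Z below 0 | 76.6% to 80.1% (79.6% at half) |
| Conditional power below 20% under the observed trend | 69.7% to 76.0% (74.5% at half) |

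With r = 0.2, the stop at Z below 0 at half information gives 81.0%.

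**7. Direction.** With a non-binding stop the final critical value is the same. Rejecting with the stop means passing the interim and also rejecting at the end. The probability of both cannot exceed the probability of rejecting at the end alone. Removing the stop therefore keeps or raises power, and the type 1 error of the final test remains 5%.

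**The case for a change.** The strongest case for acting concerns provenance. The futility clause is current SAP text, it contradicts the section directly before it, and the documents do not show which design produced 86. On the stated SDs alone, 86 is the smallest number that reaches 80% in a fixed design. A strict futility rule, such as low conditional power under the observed trend, would have pulled power well below 80% unless baseline MMDs explained a good part of the variance. SAP Section 17 also lets blinded reviews look at the sample size assumptions, and those reviewing should know what the assumptions are.

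The contradiction in wording stands, and so does the fact that the origin of the 86 cannot be settled from the documents. The step to a wrong power figure does not follow. Both texts claim at least 80%, which is an inequality that one sample size can satisfy for both designs. A lenient rule costs less than a point, and a modest baseline correlation leaves room for more. With 10000 runs the Monte Carlo standard error is sqrt(0.8 × 0.2 / 10000) = 0.4 points, so a small cost would not show in the sponsor's result. The clause may also be an accurate account, in the past tense, of how the number was found while the futility interim was still planned.

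The worry about a hidden look has an answer in the documents: the protocol's change summary and SAP Section 18 both say that there is none.

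**Conclusion.** The concern does not call for a change. The clause in SAP Section 19 is a clerical leftover from a futility interim that has been dropped. For the design being run, the stated inputs reproduce 86 per arm and a total of 230. Power is 80.1% to 80.3% by formula, and 79.5% by simulation, before any gain from the baseline covariate. If the 86 was found with a non-binding futility stop in place, true power without it is the same or higher.

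This rests on the within-population SD of 5.51 being the right one for a model with population as a factor, and on the dropped rule having been non-binding, as the protocol says. Under the less apt SD of 5.6 the shortfall is about one point, and a baseline correlation of 0.2 adds about 1.4 points (81.7% against 80.3%).

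Deleting the clause, or stating the residual SD and the baseline correlation, would make the text tidier. It would not alter the sample size, the power claim, the test or the reading of the result.
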